APPENDIX 2: TUBERCULOSIS SCREENING

All subjects must undergo screening for a history of TB infection and testing for latent/active TB infection. Their medical history review must include specific questions about a history of TB or known occupational or other personal exposure to individuals with active TB. Subjects should be asked about past testing for TB, including chest radiograph results and results of interferon-gamma release assay (IGRA, eg, QuantiFERON-TB Gold In-Tube, T-SPOT TB) or response to tuberculin skin test (TST) and history of Bacillus Calmette-Guérin vaccination.

- a. Subjects without a history of latent or active TB who have a negative IGRA or TST result at screening are eligible to enroll in the study.
- b. A TB questionnaire will be completed for all subjects (refer to questionnaire below) during the Screening period.
- c. For subjects residing in countries with a high burden of TB or MDR TB as identified by WHO, the TB screening questionnaire will be completed at every study visit (per protocol schedules of assessments). For subjects who are receiving TB prophylaxis treatment the TB questionnaire will be completed at every study visit (until TB prophylaxis treatment course is completed). This questionnaire will monitor for any emergent symptoms of active TB and compliance with any TB prophylaxis treatment.
 - For a complete list of TB high burden and MDR TB high burden countries during the period 2016 to 2020, visit:
 - <http://www.stoptb.org/countries/tbdata.asp>
 - https://www.who.int/tb/publications/global_report/high_tb_burdencountrylists/2016-2020.pdf?ua=1
- d. The IGRA or TST is NOT required at screening (or annually) for subjects with a history of active/latent TB infection.
 - Subjects with past or current history of active TB, regardless of treatment history, are excluded from enrollment.
 - Subjects with a history of latent TB infection diagnosed prior to screening must have documentation of treatment with at least four weeks of an acceptable TB prophylaxis treatment regimen to qualify for enrollment. It is the responsibility of the investigator to verify the adequacy of previous TB treatment and provide appropriate documentation (Direct Observation Therapy report where available).
- e. Acceptable TB prophylaxis treatment regimens for latent TB is defined according to local country guidelines. If no local country guidelines for the treatment of latent TB exist, WHO guidelines must be followed.

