- f. Subjects with a newly identified positive IGRA (one retest is allowed with approval from the Medical Monitor per Section 9.3.1) or TST result at Screening must be considered a Screen Failure, however they are eligible for rescreening once they undergo an evaluation to rule out active TB (chest x-ray to rule out pulmonary TB) and initiate an acceptable TB prophylaxis treatment regimen for latent TB at least 4 weeks prior to rescreening (with a plan to complete the TB treatment course during study participation) before they can be considered for enrollment. For subjects

diagnosed with latent TB infection and reside in countries with high burden of TB or MDR TB: A chest CT scan should be performed to rule out current/past pulmonary TB in the event the chest X-ray is equivocal.

- g. An assessment of adequacy of the TB prophylaxis treatment regimen and duration of treatment must be performed by an infectious disease consultant or physician TB expert.
- h. IGRA and TST interpretation
 - Subjects will be considered to have a negative diagnostic test for TB if at least one of the following circumstances applies:
 - Negative QuantiFERON-TB Gold test.
 - Combination of a negative QuantiFERON-TB Gold test and negative purified protein derivative (PPD) TST (in countries where IGRA is not considered a validated test).
 - A combination of two indeterminate QuantiFERON-TB Gold tests and a negative PPD TST (in countries where IGRA is not considered a validated test). An indeterminate IGRA test result should be repeated. In the event that the second IGRA test result is also indeterminate, the subject may be enrolled without treatment for latent TB if his/her chest radiograph shows no abnormality suggestive of TB (active or old, inactive TB) and the subject has no additional risk factors for TB as determined by a physician TB expert physician.
 - If the IGRA is not considered a validated test or is not registered for use in the subject's country, a negative TST result is required to rule out latent TB infection.
 - A positive TST reaction is ≥ 10 mm of induration, or ≥ 5 mm of induration for subjects receiving equivalent of prednisone > 15 mg/day for any medical conditions and subjects residing in countries identified by WHO as a high TB burden country or high MDR TB burden country.
- i. Resources
 - For the WHO guidelines for the treatment of latent TB visit:

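### Protocol Appendix 2 gives conflicting TB eligibility rules: item h contradicts itself on the skin test, and items a and f classify discordant results in opposite ways

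*Protocol*

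**What the plan says.** Exclusion criterion 12 (Protocol Section 4.2) bars active or latent TB infection at screening and refers to Appendix 2 for how test results are interpreted. Four parts of that appendix matter here.

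- **Item a.** Subjects with no TB history "who have a negative IGRA or TST result at screening are eligible to enroll in the study".
- **Item f.** A subject with a newly identified positive IGRA "or TST result at Screening must be considered a Screen Failure". Rescreening is possible later under conditions.
- **Item h, list.** "Subjects will be considered to have a negative diagnostic test for TB if at least one of the following circumstances applies". The first circumstance is simply "Negative QuantiFERON-TB Gold test". The second is a negative QuantiFERON together with a negative TST, and the third is two indeterminate QuantiFERON results together with a negative TST. The second and third are each limited to countries where IGRA is not considered validated.
- **Item h, further text.** After a second indeterminate IGRA, "the subject may be enrolled without treatment for latent TB if his/her chest radiograph shows no abnormality suggestive of TB", provided that a TB expert also finds no additional risk factors. Separately, where IGRA is not validated or not registered, "a negative TST result is required to rule out latent TB infection".

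**The concern.** These rules control entry to up to 52 weeks of a drug that lowers circulating lymphocytes (Protocol Section 1.3). The protocol treats TB as a serious matter: latent infection at screening is exclusionary, and confirmed active TB requires treatment to stop (Section 5.1). Waivers are not allowed (Section 9.1), so sites have to apply the text as it stands.

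Two sites could each follow a sentence of Appendix 2 faithfully and reach opposite decisions on the same results. One would enrol the subject without prophylaxis, and the other would record a screen failure. Exclusion criterion 12 and footnote e of Table 7 both lead back to this appendix, and Section 9.3.1 deals only with retesting, so no other section says how discordant results are to be read.

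No endpoint, estimand, power figure or analysis depends on this. What is at stake is the safety of a small number of subjects and uniform eligibility across sites.

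**Working it through.** The plan has no figure to reproduce here. The check is logical, followed by a rough count.

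**1. Item h list.** Let Q = negative QuantiFERON, I = two indeterminate QuantiFERON results, T = negative TST, C = IGRA not validated in the country. The list says a test is negative if

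Q or (Q and T and C) or (I and T and C).

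The middle term is contained in Q, so this reduces to

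Q or (I and T and C).

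Whenever QuantiFERON is negative, the list ignores the TST.

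**2. All rules together.** I tabulated country status (IGRA validated, not validated, not registered) against QuantiFERON (negative, positive, two indeterminate, not done) and TST (negative, positive, not done). QuantiFERON was taken as not done where it is not registered. That gives 12 + 12 + 3 = 27 combinations. The chest radiograph allowance was not coded. Item a is read for a subject without TB history. The informative rows are:

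| IGRA in country | QuantiFERON | TST | Item h list | Item h TST sentence | Item a | Item f |
|---|---|---|---|---|---|---|
| Validated | Negative | Positive | Negative | Not applicable | Eligible | Screen failure |
| Validated | Positive | Negative | Not negative | Not applicable | Eligible | Screen failure |
| Not validated | Negative | Positive | Negative | Not met | Eligible | Screen failure |
| Not validated | Negative | Not done | Negative | Not met | Eligible | Not triggered |
| Not validated | Positive | Negative | Not negative | Met | Eligible | Screen failure |
| Not validated | Two indeterminate | Negative | Negative | Met | Eligible | Not triggered |
| Not validated | Two indeterminate | Positive | Not negative | Not met | Not eligible | Screen failure |

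- Removing the second circumstance changes the result in 0 of 27 combinations.
- Item h contradicts itself in 2 combinations: IGRA not validated, QuantiFERON negative, TST positive or not done.
- Items a and f conflict in 4 combinations, covering both directions of discordance.
- With two indeterminate results where IGRA is not validated, the TST does decide the list result (last two rows).

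**3. Two indeterminate results.** The third circumstance asks for a negative TST. The sentences after it allow enrolment on a clear radiograph and no added risk factors, and do not mention the TST. Nothing says whether both sets of conditions must hold or either is enough.

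**4. Size.** The planned total is 420. The documents give neither the share of subjects in countries where IGRA is not validated or registered nor the rates of discordant or indeterminate results. I assume a country share of 2% to 10%, of whom 5% to 15% are IGRA-negative and TST-positive, or 1% to 5% have two indeterminate IGRAs.

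- Discordant: 420 × 0.02 × 0.05 = 0.42 to 420 × 0.10 × 0.15 = 6.3, so about 0 to 6 subjects.
- Two indeterminate: 420 × 0.02 × 0.01 = 0.084 to 420 × 0.10 × 0.05 = 2.1, so about 0 to 2 subjects.

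The first range counts one direction of discordance only. It leaves out discordance where IGRA is validated and a TST is done anyway.

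**The case against.** A sensible site can find a workable reading: QuantiFERON alone where IGRA is validated, and a negative TST as well where it is not. The country limits on the second and third circumstances point that way. Item f and the TST sentence are worded as obligations, whereas item a reads as a general statement that may simply mean whichever test was done. Discordance needs two tests. A TST is not required where IGRA is validated, and Table 6 lists only QuantiFERON among the screening laboratory tests. There are other safeguards: exclusion criterion 12 itself, a chest X-ray and a TB questionnaire for every subject at screening, an option on the questionnaire to refer to a TB expert, Medical Monitor approval of retests, and the expert's judgement in the radiograph route.

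Much of this stands. It makes a wrong enrolment less likely and confines the problem mainly to countries where IGRA is not validated. It does not remove the contradiction, because the workable reading requires the site to add a country limit to the first circumstance that the text lacks, and to give item f priority over item a when no priority is stated. The bullet levels in item h could also be read differently. Even if the TST sentence belonged inside the list, the conflict between item a, the first circumstance and item f would remain.

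A reader might go further and infer that the skin-test requirement never operates. The documents do not support that. The TST decides the third circumstance, it is the deciding test where IGRA is not registered and only a TST is done, and a positive TST triggers item f. The TST sentence is contradicted by the list, not cancelled by it. A reader might also apply the 1% to 5% indeterminate rate to all 420 subjects and get 4 to 21. That overstates the count, because the third circumstance applies only where IGRA is not validated; elsewhere those subjects do not face that pair of rules.

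**Conclusion.** The point holds as a contradiction between stated rules. One circumstance in item h is redundant. The first circumstance conflicts with the TST sentence in the same item. Items a and f give opposite outcomes when both tests are done and disagree. The rule for two indeterminate IGRAs, where IGRA is not validated, leaves open how its two sets of conditions combine. These conclusions follow from the wording and need no assumed rates.

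The scale is small: about 0 to 6 subjects for discordant results and about 0 to 2 for two indeterminate results, resting entirely on the assumed ranges. It is worth correcting because the rule is a safety gate and the remedy is cheap. Trial results would not be affected.

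**What to change.** Reconcile items a, f and h of Appendix 2:

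- Limit each circumstance in item h to a stated country class (IGRA validated and registered, or not), so that no circumstance contains another and none conflicts with the TST sentence.
- Have item a refer to a negative diagnostic test as defined in item h, in place of its present either-test wording.
- State one outcome for discordant results in each direction, and say which item takes precedence.
- State one outcome for two indeterminate IGRAs, and say whether the TST and radiograph conditions are cumulative or alternative.

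Which outcome applies in each case is a clinical decision for the sponsor's TB experts. The cost is a wording change to the appendix or a clarification memo to sites, with no procedure beyond those the appendix already names.

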APPENDIX 3: MAYO CLINIC SCORE – SAMPLE

Mayo Scoring System for Assessment of Ulcerative Colitis Activity

Stool frequency^a

- 0 = Normal number of stools for this subject
 - 1 = 1 to 2 stools more than normal
 - 2 = 3 to 4 stools more than normal
 - 3 = 5 or more stools more than normal
- Subscore: 0 to 3

Rectal bleeding^b

- 0 = No blood seen
 - 1 = Streaks of blood with stool less than half the time
 - 2 = Obvious blood with stool most of the time
 - 3 = Blood alone passes
- Subscore: 0 to 3

Findings on endoscopy^c

- 0 = Normal or inactive disease
 - 1 = Mild disease (erythema, decreased vascular pattern)
 - 2 = Moderate disease (marked erythema, lack of vascular pattern, friability, erosions)
 - 3 = Severe disease (spontaneous bleeding, ulceration)
- Subscore: 0 to 3

Physician's Global Assessment^d

- 0 = Normal
 - 1 = Mild disease
 - 2 = Moderate disease
 - 3 = Severe disease
- Subscore: 0 to 3

The Mayo score ranges from 0 to 12, with higher scores indicating more severe disease.

a Each subject serves as his or her own control to establish the degree of abnormality of the stool frequency.

b The daily bleeding score represents the most severe bleeding of the day.

c The endoscopy subscore will be determined by qualified personnel at a central laboratory.

d The Physician's Global Assessment acknowledges the 3 other criteria, the subject's daily recollection of abdominal discomfort and general sense of well-being, and other observations, such as physical findings and the subject's performance status.

APPENDIX 4: HISTOLOGICAL SCORING INDICES

Geboes Grading System

The Geboes Grading System is a stepwise grading system used for the evaluation of microscopic inflammation and histopathologic disease activity in UC. The microscopic appearance of the mucosa is categorized into 6 grades. A decrease of the Geboes Score grading system to Grade zero (0) or one (1) indicates mucosal healing ([Geboes 2000](#)).

Nancy Histological Index

The Nancy Histological Index is a validated index for assessing histological disease activity in UC. It is composed of three histological items defining five grades of disease activity: absence of significant histological disease (grade 0), chronic inflammatory infiltrate with no acute inflammatory infiltrate (Grade 1), mildly active disease (Grade 2), moderately active disease (Grade 3), and severely active disease (Grade 4). The presence of ulceration on the biopsy specimen corresponds to severely active disease (Grade 4). If there is no ulceration, acute inflammatory cells infiltrate (presence of neutrophils) is assessed. Moderate or severe acute inflammatory cells infiltrate corresponds to moderately active disease (Grade 3), while mild acute inflammatory cells infiltrate correspond to mildly active disease (Grade 2). If there is no acute inflammatory cells infiltrate, assessment of chronic inflammatory infiltrate (lymphocytes and plasmacytes) is made. A biopsy specimen showing moderate or marked chronic inflammatory infiltrate corresponds to moderate or marked chronic acute inflammatory infiltrate (Grade 1). A biopsy specimen showing mild or no chronic inflammatory infiltrate corresponds to absence of significant histological disease (Grade 0) ([Marchal-Bressenot 2017](#)).

Robarts Histopathology Index

[figure not shown]
The Robarts Histopathology Index (RHI) is an evaluative index, derived from the Geboes score, that is designed to be reproducible and responsive to clinically meaningful change in disease activity over time. The total RHI score ranges from 0 (no disease activity) to 33 (severe disease activity) and is calculated as follows: $RHI = 1 \times \text{Chronic inflammatory infiltrate} + 2 \times \text{Lamina propria neutrophils} + 3 \times \text{Neutrophils in epithelium} + 5 \times \text{Erosion or ulceration}$ ([Mosli 2017](#)).

APPENDIX 5: GUIDANCE FOR THE ASSESSMENT OF POTENTIAL PROGRESSIVE MULTIFOCAL LEUKOENCEPHALOPATHY

If a subject exhibits signs and symptoms suspicious for PML, the Investigator must interrupt study treatment and perform a targeted neurologic examination to assess for signs of PML, which are diverse, progress over days to weeks, and may include progressive weakness on one side of the body or clumsiness of limbs or difficulty with walking or writing or fine motor skills, disturbance of vision, changes in thinking, memory and orientation leading to confusion and (expressive aphasia), and/or agnosia (receptive aphasia). Consultation with a local neurologist may be warranted, as presented in the PML case evaluation algorithm in [Figure 2](#).

The Medical Monitor should be informed of any suspected cases of PML and, if needed, will facilitate investigator/local neurologist consultation with PML medical experts on the independent adjudication committee.

Figure 2: Progressive Multifocal Leukoencephalopathy Case Evaluation Algorithm

CE, contrast-enhanced; CSF, cerebral spinal fluid; IAC, independent adjudication committee; IP, investigational product; JCV, John Cunningham Virus; MRI, magnetic resonance imaging; PCR, polymerase chain reaction; PML, progressive multifocal leukoencephalopathy; r/o, rule out.

Note: IP dosing may resume, and no further evaluation is needed if the Investigator assessment reveals no objective signs of PML, the local neurologist confirms that the subject does not have PML, or the IAC's review of the evidence concludes that PML is ruled out.

Summary of Changes

| Section No. and Name | Description of Change | Brief Rationale |
|-------------------------------------------------------------------------------------------------------------------------------------------------------------------------|------------------------------------------------------------------------------------------------------------------------------------------------------------------------------------------------------------------------------------------------------------------------------------------------------------------------------------------------------------------------------------------------------------------------------------------------------------------------------------------------------------------------------------------------------------------------------------------------|-----------------------------------------------------------------------------------------------------------------------------------------------------------|
| Throughout | Minor editorial, formatting, and nomenclature revisions | Minor; therefore, have not been summarized |
| Synopsis: Study Design Synopsis: Statistical methods 3.1. Summary of Study Design 6.4. Method of Assigning Subjects to Treatment 10.12.1. Efficacy Analysis | Changed the first stratification factor from “failed biologic/JAK inhibitor therapy (yes/no)” to “naïve to biologic or JAK inhibitor therapy at study entry (yes/no)” | The terminology was changed from “failed” to “naïve” because the term “naïve” was originally intended when the protocol was written. |
| 4.1. Inclusion Criteria: Prior treatment failure criteria: Inadequate response | Deleted the word “induction” from the description of prior therapy | The criterion applies to any regimen; not limited to induction |
| 4.1. Inclusion Criteria: Prior treatment: Loss of response | Deleted “approved maintenance dosing” from prior treatment description | For clarification |
| Synopsis: “ Other general inclusion criteria ” 4.1. Inclusion Criteria: Other general inclusion criteria : | Updated criteria for hematological function | Given the mechanism of action of the drug in reducing peripheral lymphocytes, these changes in hematologic parameters may be important for safety reasons |
| 5.1. Discontinuation of Study Treatment | Added: 
 Subjects will be discontinued from the study treatment if they experience a cardiovascular treatment-related symptomatic event (eg, chest pain, dizziness, palpitations, lightheadedness, shortness of breath, or syncope) associated with reduction of heart rate with clinically relevant ECG changes at any time during the post-dose 4-hour monitoring period. Subjects who have not met the discharge criteria (Table 4) on Day 1 after ≥ 4 hours of extended monitoring, or Day 2 by 4 hours post-dose | Added as an extra safety precaution |

| Section No. and Name | Description of Change | Brief Rationale |
|------------------------------------------------------------------------------------------|-----------------------------------------------------------------------------------------------------------------------------------------------------------------------------------------------------------------------------------------------------------------------|-------------------------------------------------------------------------------------------|
| 5.1.1. Discontinuation from Double-Blind Treatment for Disease Worsening | Updated language specifying criteria for entry into the APD334-303 open-label extension study | To provide more clarity and guidance to Investigators |
| 6.3.1. Instructions for Missed Dose(s) | Deleted instruction that vomiting of the tablet should be recorded in the subject's electronic diary (eDiary). | It is not intended that subjects record vomiting of study treatment |
| 6.3.2. Dose Interruptions | Moved the description of symptoms and treatment for PML from Section 6.3.2 to Section 9.9.8.1.4 (Adverse Events of Special Interest). | Aligns the topic of the text with the Section header. |
| 9.3.5. Prior and Ongoing Therapies | Modified text to state documentation of prior UC therapies should include the prior treatment response as one of the following: inadequate response to, loss of response to, or intolerance to | For proper documentation of response to prior UC therapies |
| 9.3.10. Proctosigmoidoscopy/ Colonoscopy and Modified Mayo Score Derivation | For SF changed from "baseline" to "normal" | For consistency with Section 9.7.1 and for more appropriate description of the assessment |
| 9.4.2.1. Guidance for Cardiac Monitoring Following Treatment Initiation or Re Initiation | Added new Section "Guidance for Cardiac Monitoring Following Treatment Initiation or Re-Initiation," with details relating to first dose cardiac monitoring, extended cardiac monitoring, and study treatment discontinuation related to post-dose cardiac monitoring | To provide additional guidance and details for vital sign and cardiac monitoring |
| 9.7.1. Modified Mayo Score/Mayo Clinic Score | Deleted that stool frequency before initial onset of signs and symptoms of UC to be used as the reference SF would be recorded in the subject's eDiary | This will be recorded at screening in the eCRF, not in the subject's eDiary. |
| 9.7.1.2. Endoscopic Biopsies | Modified the language on the biopsy location to specify collection from the most affected area 15 to 25 cm from the anal verge | To provide additional guidance |
| 9.9.8.1.2. Serious Adverse Event | Deleted "Admission to a palliative unit or hospice care facility is not considered to be a hospitalization. Hospitalizations or prolonged hospitalizations for scheduled therapy of the underlying cancer or study | Not relevant to this protocol |

| Section No. and Name | Description of Change | Brief Rationale |
|----------------------------------------------------------|-----------------------------------------------------------------------------------------------------------------------------------------------------------------------------------------------------------------------------------------------------------------------------------------------------------------------------------------------------------|--------------------------------------------------------------------------------------------------------------------------------------------------------------------------------------------------------------------------------------------------------------------------|
| | target disease need not be captured as SAEs” from the definition of SAE | |
| 9.9.8.2.2. Recording Adverse Events | Updated language that SAEs should be described in the narrative description field of the eCRF | To provide more clarity and guidance to Investigators and to align with updates in the Protocol template |
| 9.9.8.3.1. Serious Adverse Events | Added contact information for reporting of SAEs | To provide more clarity and guidance to Investigators |
| 9.10. Procedures for Overdose | Added new section | Provide information for investigators relating to subject overdose. |
| 10.3. Analysis Sets | Renamed the analysis sets as follows: 
 • Intent-to-treat population renamed Full Analysis Set (FAS) • Modified intent-to-treat population renamed Modified Full Analysis Set (mFAS) • Per-protocol population renamed Per Protocol Set • Safety population renamed Safety Set | For consistency with FDA Guidance “E9 Statistical Principles for Clinical Trials ” (Section V. B. 1.), ICH E9 “ Statistical Principles ” (Section 5.2), and EMEA Guidance “ICH Topic 39 Statistical Principles for Clinical Trials ” (Section V.2). |
| 10.10. Subgroup Analyses | Added new section describing subgroup analyses | Sponsor decision |
| Table 7, Schedule of Assessments, 12-lead ECG row | Added a 12-lead ECG at the Week 12/Early Termination visit. | Sponsor decision |
| Table 7, Schedule of Assessments, Footnote “a” | Modified text to clarify that for subjects who complete Week 12 and are eligible to enter the APD334 303 OLE study, the Week 12 visit will be used to assess eligibility for the OLE and may also serve as the Day 1 visit of the OLE | For clarification and guidance for Investigators |
| Table 7, Schedule of Assessments, Footnote “k” | Rewrote to be consistent with new cardiac monitoring text | For document consistency |

| Section No. and Name | Description of Change | Brief Rationale |
|-------------------------------------------------|-------------------------------------------------------------------------------------------------------------------------------------------------------------------|----------------------------------------------------------------------------------------|
| Table 8, Schedule of Assessments, Footnote “a” | Modified text to clarify that the Week 52/Early Termination visit will be used to assess eligibility for the OLE and may also serve as the Day 1 visit of the OLE | For clarification and guidance for Investigators |
| Table 8, Schedule of Assessments | Added an additional row entitled “12-lead ECG”, indicating that a 12-lead ECG will be conducted at the Week 52/Early Termination visit. | Sponsor decision |
| Appendix 5: Investigator Signature Page | Updated to new signature page format | Formatting revision |
| Added Appendix 6: Country Specific Requirements | Insertion of Sponsor signature page for a hand-written signature | To meet signature requirements in countries that do not recognize electronic signature |

CLINICAL STUDY PROTOCOL SUMMARY OF CHANGES

Protocol title: A Phase 3, Randomized, Double-Blind, Placebo-Controlled, 52-Week Study to Assess the Efficacy and Safety of Etrasimod in Subjects with Moderately to Severely Active Ulcerative Colitis

Protocol number: APD334-301

Version: Amendment 2.0, 20 December 2019

Replaces version: Amendment 1, 05 March 2019

Confidentiality Statement

This document contains confidential information of Arena Pharmaceuticals, Inc. Unauthorized distribution, copying, or disclosure is strictly prohibited unless required by applicable law. Persons receiving this information must be notified that it is confidential and may not be further distributed, copied, or disclosed.

PROTOCOL AMENDMENT SUMMARY OF CHANGES

Amendment 2.0, 20 December 2019

This amendment is considered to be substantial based on the criteria set forth in Article 10(a) of Directive 2001/20/EC of the European Parliament and the Council of the European Union because it significantly impacts the safety or physical/mental integrity of subjects.

Overall Rationale for the Amendment

The overall rationale for this amendment is to address update criteria for early (ie, prior to Week 52) enrollment in the open-label study and eligibility criteria (eg, list of prior therapy failures or non-response, contraception use, cardiovascular disease history, and prior therapy washout period). Additional instructions for safety monitoring related to 12-lead electrocardiogram, pulmonary function tests, and ophthalmoscopy and optical coherence tomography testing. Further instructions for Quantiferon TB Gold and tuberculin skin test were added. In addition, a 4-Week Follow-Up visit was added.

Summary of Changes

| Section No. and Name | Description of Change | Brief Rationale |
|---------------------------------------------------------------------------------------------------------|---------------------------------------------------------------------------------------------------------------------------------------------------------------------------------------------------------------------------------------------------------------|--------------------------------------------------------------------------------------------------------------------------------------------------|
| Throughout | Minor editorial, formatting, and nomenclature revisions | Minor and do not affect the conduct of the protocol; therefore, have not been summarized |
| Title Page | Added NCT number | Administrative change |
| | Updated title of Sponsor's Responsible Medical Officer to: [REDACTED] [REDACTED] | Administrative change due to organizational update |
| | Updated Amendment 2.0 Version date: 20 December 2019 | Administrative change |
| | Added Protocol History table | To summarize protocol amendment history |
| Synopsis: Study design 3.1. Summary of Study Design | Removed "Randomized subjects who experience UC exacerbation during the 12 Week Treatment Period will be considered as having a treatment nonresponse and should be managed according to the local standard of care." | For additional clarity and guidance to Investigators |
| Synopsis: Study design 3.1. Summary of Study Design | Revised entry criteria into open-label extension starting at the Week 12 visit and continuing through the 40-Week Treatment Period for subjects who experience UC worsening | To provide greater clarity |
| 3.3. Study Duration | Added "The End of Study is the date when the last subject completes his/her last study visit." | For additional clarity and guidance to Investigators |
| Synopsis: Eligibility criteria: Inclusion Criterion 1 4.1. Inclusion Criteria: Inclusion Criterion 1 | Added "Enrollment of subjects < 18 years should be conducted only if acceptable according to local laws and regulations" | To satisfy local regulations that allow inclusion of minors (under 18 years) in clinical trials only after the results from adults are available |
| Synopsis: Eligibility criteria: Inclusion Criterion 4 4.1. Inclusion Criteria: Inclusion Criterion 4 | Changed to state "Subjects with proctitis only at baseline who meet the other eligibility criteria for inclusion, including the endoscopic and rectal bleeding criteria for moderate to severe disease, will be capped at 15% of the total subjects enrolled" | For additional clarity and guidance to Investigators |

| Section No. and Name | Description of Change | Brief Rationale |
|-------------------------------------------------------------------------------------------------------------------------------------------------------------------------------|-----------------------------------------------------------------------------------------------------------------------------------------------------------------------------------------------|---------------------------------------------------------------------------------------------------------------------|
| Synopsis: Eligibility criteria: Inclusion Criterion 6 4.1. Inclusion Criteria: Inclusion Criterion 6 | Added “according to routine practice” to removal of any adenomatous polyps | For clarification on eligibility criteria |
| Synopsis: Eligibility criteria: Inclusion Criterion 7 4.1. Inclusion Criteria: Inclusion Criterion 7 | Added interleukin 12/23 antibodies (eg, ustekinumab) to list of biologic therapies for JAK inhibitor therapies | Added due to recent FDA approval for treatment of moderately to severely active ulcerative colitis |
| | Added to note regarding qualifying therapy that “the subject must have received an adequate course of therapy based on local guidelines for that therapy” | To ensure that subjects had received adequate prior qualifying therapy |
| Synopsis: Eligibility criteria: Inclusion Criteria 9 and 10 4.1. Inclusion Criteria: Inclusion Criteria 9 and 10 | Vital signs and screening ECG have been deleted | Now covered in new Exclusion Criterion 8 |
| Synopsis: Eligibility criteria: Inclusion Criterion 10 (formerly Inclusion Criterion 12) 4.1. Inclusion Criteria: Inclusion Criterion 10 (formerly Inclusion Criterion 12) | Updated adequate hepatic function for ALT and AST to levels $\leq 2.0 \times \text{ULN}$ (from levels $\leq 3.0 \times \text{ULN}$) | Extra safety precaution |
| Synopsis: Eligibility criteria: Inclusion Criterion 12 (formerly Inclusion Criterion 15) 4.1. Inclusion Criteria: Inclusion Criterion 12 (formerly Inclusion Criterion 15) | Updated contraception language | To be in accordance with the contraception guidance from Clinical Trials Facilitation and Coordination Group (CTFG) |
| Synopsis: Eligibility criteria: Exclusion Criterion 7 4.2. Exclusion Criteria: Exclusion Criterion 7 | Deleted hematologic, hepatic, pulmonary, and ophthalmological conditions from criterion. Alcohol/drug abuse/dependence (formerly Exclusion Criterion 21) and cognitive impairment were added. | Covered in other specific exclusion criteria |

| Section No. and Name | Description of Change | Brief Rationale |
|-------------------------------------------------------------------------------------------------------------------------------------------------------------------------------|-------------------------------------------------------------------------------------------------------------------------------------------------------------------------------------------------------------------------------------------------------------------------------------------------------------------------------|------------------------------------------------------------------------------------------------------------------------------------------------|
| Synopsis: Eligibility criteria: Exclusion Criteria 8 and 9 4.2. Exclusion Criteria: Exclusion Criteria 8 and 9 | Combined Exclusion criteria 8 and 9 and updated the criterion for cardiovascular function exclusion | To be in compliance with the precautions mentioned in previous study protocols submitted in France and in line with the fingolimod information |
| Synopsis: Eligibility criteria: Exclusion Criterion 8 4.2. Exclusion Criteria: Exclusion Criterion 8 and throughout | Updated PR interval criterion from ≤ 200 ms for inclusion to > 200 ms for exclusion | More appropriately fits within new cardiovascular function exclusion criterion |
| Synopsis: Eligibility criteria: Exclusion Criterion 12 4.2. Exclusion Criteria: Exclusion Criterion 12 (formerly Inclusion Criterion 13) | Updated TB exclusion criterion language | For greater clarity and additional guidance to Investigators and to harmonize with programmatic language |
| Synopsis: Eligibility criteria: Exclusion Criterion 13 (formerly Exclusion Criterion 14) 4.2. Exclusion Criteria: Exclusion Criterion 13 (formerly Exclusion Criterion 14) | Updated and modified active infection exclusion criterion to “ ≤ 28 days prior to randomization, required intravenous medication ≤ 14 days prior to randomization, or that may worsen (in the opinion of the Investigator) if the subject is treated with a drug having immunosuppressant effects (ie, etrasimod).” | To better define infection source as any active infection |
| Synopsis: Eligibility criteria: Exclusion Criterion 17 4.2. Exclusion Criteria: Exclusion Criterion 17 | Updated and modified history of opportunistic infection exclusion criterion to “History of an opportunistic infection (eg, Pneumocystis jirovecii , cryptococcal meningitis, progressive multifocal leukoencephalopathy) or history of disseminated herpes simplex or disseminated herpes zoster.” | To better define infection history |
| Synopsis: Eligibility criteria: Exclusion Criterion 21 4.2. Exclusion Criteria: Exclusion Criterion 21 | Added “21. Hypersensitivity to etrasimod or any of the excipients or placebo compounds” as a new exclusion criterion | Added at the request of regulatory authorities. All subsequent exclusion criteria were renumbered accordingly. |
| Synopsis: Eligibility criteria: Exclusion Criterion 21 4.2. Exclusion Criteria: Exclusion Criterion 21 | Deleted criterion and moved to Exclusion Criterion 7 | To avoid redundancies |

| Section No. and Name | Description of Change | Brief Rationale |
|------------------------------------------------------------------------------------------------------------------------------------------------------------------------------------------|-----------------------------------------------------------------------------------------------------------------------------------------------------------------------------------------------------------------------------------------------------------|------------------------------------------------------------------------------------------------------|
